### 7.2.2 Pembrolizumab Dose Modification

AEs associated with pembrolizumab exposure may represent an immunologic etiology. These immune-related AEs (irAEs) may occur shortly after the first dose or several months after the last dose of pembrolizumab treatment and may affect more than one body system simultaneously. Therefore, early recognition and initiation of treatment is critical to reduce complications. Based on existing clinical study data, most irAEs were reversible and could be managed with interruptions of pembrolizumab, administration of corticosteroids and/or other supportive care. For suspected irAEs, ensure adequate evaluation to confirm etiology or exclude other causes. Additional procedures or tests such as bronchoscopy, endoscopy, skin biopsy may be included as part of the evaluation. Based on the severity of irAEs, withhold or permanently discontinue pembrolizumab and administer corticosteroids. Dose modification and toxicity management guidelines for irAEs associated with pembrolizumab are provided in Table 4

04W5XD

Table 4 Dose Modification and Toxicity Management Guidelines for Immune-related AEs Associated with Pembrolizumab

### **General instructions:**

1. Corticosteroid taper should be initiated upon AE improving to Grade 1 or less and continue to taper over at least 4 weeks.

2. For situations where pembrolizumab has been withheld, pembrolizumab can be resumed after AE has been reduced to Grade 1 or 0 and corticosteroid has been tapered. Pembrolizumab should be permanently discontinued if AE does not resolve within 12 weeks of last dose or corticosteroids cannot be reduced to ≤10 mg prednisone or equivalent per day within 12 weeks.

3. For severe and life-threatening irAEs, IV corticosteroid should be initiated first followed by oral steroid. Other immunosuppressive treatment should be

initiated if irAEs cannot be controlled by corticosteroids.

Immune-related AEs	Toxicity grade or conditions (CTCAEv4.0)	Action taken to pembrolizumab	irAE management with corticosteroid and/or other therapies	Monitor and follow-up
Pneumonitis	Grade 3 or 4, or recurrent grade 2	Withhold  Permanently discontinue	Administer     corticosteroids (initial     dose of 1-2mg/kg     prednisone or     equivalent) followed by     taper	
 
Monitor participants for signs and symptoms of pneumonitis
 
Evaluate participants with suspected pneumonitis with radiographic imaging and initiate corticosteroid treatment
 
Add prophylactic antibiotics for opportunistic infections
 

Diarrhea / colitis	Grade 2 or 3	Withhold	Administer     corticosteroids (initial     dose of 1-2mg/kg     prednisone or     equivalent) followed by     taper	Monitor participants for signs and symptoms of enterocolitis (i.e. diarrhea, abdominal pain, blood or mucus in stool with or without fever) and of bowel perforation (i.e.
	Grade 4	Permanently discontinue		
 
peritoneal signs and ileus).
 
Participants with ≥ Grade 2 diarrhea suspecting colitis should consider GI consultation and performing endoscopy to rule out colitis.
 
Participants with diarrhea/colitis should be advised to drink liberal quantities of clear fluids. If sufficient oral fluid intake is not feasible, fluid and electrolytes should be substituted via IV infusion.
 

MK-7123-034-01 Final Protocol

Confidential

22-Mar-2018

### **General instructions:**

1. Corticosteroid taper should be initiated upon AE improving to Grade 1 or less and continue to taper over at least 4 weeks.

- 2. For situations where pembrolizumab has been withheld, pembrolizumab can be resumed after AE has been reduced to Grade 1 or 0 and corticosteroid has been tapered. Pembrolizumab should be permanently discontinued if AE does not resolve within 12 weeks of last dose or corticosteroids cannot be reduced to ≤10 mg prednisone or equivalent per day within 12 weeks.
- 3. For severe and life-threatening irAEs, IV corticosteroid should be initiated first followed by oral steroid. Other immunosuppressive treatment should be initiated if irAEs cannot be controlled by corticosteroids.

Immune-related AEs	Toxicity grade or conditions (CTCAEv4.0)	Action taken to pembrolizumab	irAE management with corticosteroid and/or other therapies	Monitor and follow-up
AST / ALT elevation or increased bilirubin	Grade 2	Withhold	Administer corticosteroids (initial dose of 0.5- 1mg/kg prednisone or equivalent) followed by taper	Monitor with liver function tests (consider weekly or more frequently until liver enzyme value returned to baseline or is stable)
	Grade 3 or 4	Permanently discontinue	Administer     corticosteroids (initial     dose of 1-2mg/kg     prednisone or     equivalent) followed by     taper	
Type 1 diabetes mellitus (T1DM) or Hyperglycemia	Newly onset T1DM or Grade 3 or 4 hyperglycemia associated with evidence of β-cell failure	Withhold	
 
Initiate insulin replacement therapy for participants with T1DM
 
Administer antihyperglycemic in participants with hyperglycemia
 
	Monitor participants for hyperglycemia or other signs and symptoms of diabetes.
Hypophysitis	Grade 2 Grade 3 or 4	Withhold or permanently discontinue 	Administer     corticosteroids and     initiate hormonal     replacements as     clinically indicated.	Monitor for signs and symptoms of hypophysitis (including hypopituitarism and adrenal insufficiency)

### **General instructions:**

- 1. Corticosteroid taper should be initiated upon AE improving to Grade 1 or less and continue to taper over at least 4 weeks.
- 2. For situations where pembrolizumab has been withheld, pembrolizumab can be resumed after AE has been reduced to Grade 1 or 0 and corticosteroid has been tapered. Pembrolizumab should be permanently discontinued if AE does not resolve within 12 weeks of last dose or corticosteroids cannot be reduced to ≤10 mg prednisone or equivalent per day within 12 weeks.
- 3. For severe and life-threatening irAEs, IV corticosteroid should be initiated first followed by oral steroid. Other immunosuppressive treatment should be initiated if irAEs cannot be controlled by corticosteroids.

Immune-related AEs	Toxicity grade or conditions (CTCAEv4.0)	Action taken to pembrolizumab	irAE management with corticosteroid and/or other therapies	Monitor and follow-up
Hyperthyroidism	Grade 2	Continue	Treat with non-selective beta-blockers (e.g. propranolol) or	Monitor for signs and symptoms of thyroid disorders.
	Grade 3 or 4	Withhold or permanently discontinue 	thionamides as appropriate	
Hypothyroidism	Grade 2-4	Continue	Initiate thyroid     replacement hormones     (e.g. levothyroxine or     liothyroinine) per     standard of care	Monitor for signs and symptoms of thyroid disorders.
Nephritis and renal dysfunction	Grade 2	Withhold	Administer corticosteroids	Monitor changes of renal function
	Grade 3 or 4	Permanently discontinue	(prednisone 1-2mg/kg or equivalent) followed by taper.	
Myocarditis	Grade 1 or 2	Withhold	Based on severity of AE administer	Ensure adequate evaluation to confirm etiology and/or exclude other
	Grade 3 or 4	Permanently discontinue	corticosteroids	causes

### **General instructions:**

- 1. Corticosteroid taper should be initiated upon AE improving to Grade 1 or less and continue to taper over at least 4 weeks.
- 2. For situations where pembrolizumab has been withheld, pembrolizumab can be resumed after AE has been reduced to Grade 1 or 0 and corticosteroid has been tapered. Pembrolizumab should be permanently discontinued if AE does not resolve within 12 weeks of last dose or corticosteroids cannot be reduced to ≤10 mg prednisone or equivalent per day within 12 weeks.
- 3. For severe and life-threatening irAEs, IV corticosteroid should be initiated first followed by oral steroid. Other immunosuppressive treatment should be initiated if irAEs cannot be controlled by corticosteroids.

Immune-related AEs	Toxicity grade or conditions (CTCAEv4.0)	Action taken to pembrolizumab	irAE management with corticosteroid and/or other therapies	Monitor and follow-up
All other immune-related AEs	Intolerable/ persistent Grade 2	Withhold	Based on type and severity of AE	Ensure adequate evaluation to confirm etiology and/or exclude other
	Grade 3	Withhold or discontinue based on the type of event. Events that require discontinuation include and not limited to: Gullain-Barre Syndrome, encephalitis	administer corticosteroids	causes
	Grade 4 or recurrent Grade 3	Permanently discontinue		

1. Withhold or permanently discontinue pembrolizumab is at the discretion of the investigator or treating physician.

### **NOTE:**

For participants with Grade 3 or 4 immune-related endocrinopathy where withhold of pembrolizumab is required, pembrolizumab may be resumed when AE resolves to  $\leq$  Grade 2 and is controlled with hormonal replacement therapy or achieved metabolic control (in case of T1DM).

# 7.3 Method of Treatment Assignment

Treatment allocation/randomization will occur centrally using an interactive response technology (IRT) system. There are 2 study treatment arms. Participants will be assigned randomly in a 1:1 ratio to dose Arm A and dose Arm B, respectively.

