# Treatment Crouns and Duration.

eatment Groups and Duration:										
Treatment Groups	Participants will be stratified by tumor type and randomized 1:1 to either of 2 dose level arms: Arm A will receive 30 mg navarixin orally QD + pembrolizumab 200 mg IV Q3W; Arm B will receive 100 mg navarixin orally QD + pembrolizumab 200 mg IV Q3W.									
	In Stage 1 of the study, 30 participants will be randomized to each arm. In Stage 2, barring early termination of the arm, 30 additional participants will be randomized to each arm.									
Duration of Participation	Each participant will participate in the study from the time the participant signs the informed consent form (ICF) through the final protocol-specified contact.									
	After a screening phase of up to 28 days, each participant will be assigned to receive study treatment until disease progression is radiographically documented and, when clinically appropriate, confirmed by the site per modified Response Evaluation Criteria in Solid Tumors 1.1 for immune-based therapeutics (iRECIST), unacceptable adverse event(s) (AEs), intercurrent illness that prevents further administration of treatment, Investigator's decision to withdraw the participant, noncompliance with study treatment or procedure requirements, administrative reasons requiring cessation of treatment, or until the participant has received 35 administrations (approximately 2 years) of combination treatment with navarixin and pembrolizumab. Monotherapy treatment with pembrolizumab will be allowed if navarixin treatment is withheld for ANC or febrile neutropenia.									
	After the end of treatment, each participant will be followed for the occurrence of AEs and spontaneously reported pregnancy as described under Section 9.3.									
	Participants who discontinue for reasons other than radiographic disease progression will have post-treatment follow-up imaging for disease status until disease progression is documented radiographically per RECIST 1.1 and, when clinically appropriate, confirmed by the site per iRECIST, initiating a non-study cancer treatment, withdrawing consent, becoming lost to follow-up or the end of the study. All participants will be followed by telephone									
	for overall survival until death, participant withdrawal of consent, becoming lost to follow-up or the end of the study.									

**Protocol/Amendment No.:** 034-01

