The overall design is an adaptive 2-stage design. In each arm, up to 30 participants will be enrolled in the first stage, and up to 30 participants in the second stage. In the first stage, 30 participants (with 10 per tumor type) will be enrolled in each arm (dose level). When all participants in a given arm with a given tumor type complete the first on-treatment scan at 9 weeks or when clinically indicated (see Section 9.2.1.2), a futility analysis will be conducted to determine whether that tumor type and arm will progress to Stage 2. If a tumor type passes the futility analysis (see Section 5.1.4) in Stage 1, at least 10 participants will be enrolled with that tumor type in the second stage.

Initial enrollment in each dose arm will be staggered. The first 3 participants in dose Arm A or dose Arm B will be enrolled no more frequently than 1 participant per week, to allow for peripheral neutrophil assessment between participants. Peripheral neutrophil assessment (ANC) will occur at baseline, Day 3, and Day 8 during the first cycle for all participants. Decreased ANC counts typically return to normal in 48-96 hours following dosing cessation. Standard support for oncology patients with low ANC will be considered as appropriate. See dose reduction algorithm (Section 7.2.1) for more information.

Specific procedures to be performed during the study, as well as their prescribed times and associated visit windows, are outlined in the Study SoA - Section 2. Details of each procedure are provided in Section 9 – Study Assessments and Procedures.

04W5XD

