#### **Futility Analysis** 5.1.4

An interim futility analysis for efficacy will be performed after the first 10 participants for each tumor type have at least 1 post-baseline scan assessment in each dose arm in Stage 1. If one or more responses (confirmed or unconfirmed) are observed for a tumor type in an arm (i.e.  $\geq$ 10% response rate), this tumor type may be expanded to enroll at least additional 10 participants in Stage 2, for a maximum enrollment of 60 participants in this arm across 3 tumor types. Otherwise, this tumor type may be stopped early for futility.

If the decision is made to expand a tumor type in dose Arm A to Stage 2, this tumor type in dose Arm B may be expanded to Stage 2 as well, irrespective of the number of responses as long as it has passed the safety evaluation. While the decision rule is mainly based on confirmed and unconfirmed responses, the totality of data will also be taken into account.

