#### 10.6 Statistical Methods

07WYDZ

04W5XD

This section describes the statistical methods that address the primary objectives. Methods related to secondary and exploratory objectives as well as the comparison between the t2arms will be described in the sSAP. The final analyses will be performed using data from both Stage 1 and Stage 2.

MK-7123-034-01 Final Protocol 22-Mar-2018 Confidential

91

**Product:** MK-7123 SCH 527123 **Protocol/Amendment No.:** 034-01

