### **10.6.2** Statistical Methods for Safety Analysis

Safety and tolerability will be assessed by clinical review of all relevant parameters including DLTs, AEs, SAEs, laboratory tests, vital signs, ECG measurements, and physical examinations

DLT and adverse events will be summarized by counts and frequencies for each arm. Laboratory tests, vital signs, and other safety endpoints will be summarized as appropriate (e.g., counts, percentages).

Miettinen and Nurminen's method will be used to estimate the difference between the 2 arms and its 95% confidence interval for number of participants with a DLT, number of participants with ≥1 AE and number of participants discontinuing study treatment due to an AE.

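### If a tumor type enters Stage 2 in one dose arm only, its later participants cannot be randomized 1:1, yet the between-dose safety difference is set up without separating them

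*Combined protocol and SAP*

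**What the plan says.** **Assignment.** Section 7.3 states that "Participants will be assigned randomly in a 1:1 ratio to dose Arm A and dose Arm B, respectively", and 7.3.1 stratifies by tumor type. For the second stage the synopsis says: "In Stage 2, barring early termination of the arm, 30 additional participants will be randomized to each arm". Termination of a whole arm is the only exception it names. Section 7.4 makes the study open-label.

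**Opening of Stage 2.** Section 5.1 sets the unit of decision: "a futility analysis will be conducted to determine whether that tumor type and arm will progress to Stage 2". Section 5.1.4 gives the criterion, "If one or more responses (confirmed or unconfirmed) are observed for a tumor type in an arm", under which that type may be enlarged by at least 10. It continues: "Otherwise, this tumor type may be stopped early for futility". If a type expands in Arm A, the sponsor may also expand it in Arm B whatever Arm B's response count, provided Arm B has passed its safety evaluation. No rule runs the other way. Section 10.7 repeats the gate by type and arm.

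**Analysis.** Section 10.6 says: "The final analyses will be performed using data from both Stage 1 and Stage 2". For the number of participants with a DLT, with at least one AE, and discontinuing because of an AE, 10.6.2 says: "Miettinen and Nurminen's method will be used to estimate the difference between the 2 arms and its 95% confidence interval". Section 10.5.2 defines the safety population as everyone treated, with a DLT-evaluable subset for DLTs. None of these sections mentions stratifying the difference or limiting it to participants who could have received either dose.

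**The concern.** The plan creates a situation that its own assignment rule does not cover. When a type is open in one arm only, there is nothing to randomize between. The documents do not say what the IRT then does, but the open arm is the only possible destination, and in an open-label trial that dose can be known in advance.

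These participants differ from the randomized ones in three ways that have nothing to do with dose. They come from one tumor type, they enroll later, and they may be selected with the dose in view. They enter one side of the between-dose difference for the primary safety endpoints. With no control arm, the dose contrast is the only comparison that randomization protects. Mixing in non-randomized participants weakens that protection, and the 95% interval does not show it.

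**Working it through.** **1. Reproducing the plan's figures.** Section 10.7 gives an 82% and 89% chance of continuing at true ORRs of 16% and 20%. The gate is at least 1 response in 10, so P = 1 − (1 − p)^10. This gives 0.825 and 0.893, which agree to within a point.

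Table 8 also reproduces with 10 + 10 participants per type per arm. The probability is the sum over x = 1 to 10 of Pr(x responses in the first 10) × Pr(at least r − x in the next 10), with r = 2 for CRC and r = 3 for NSCLC and prostate. The results are 1.3%, 76.7%, 6.9% and 75.9%, against the stated 1%, 77%, 7% and 76%. The planning figures therefore rest on 10 added per type.

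**2. Chance that one type passes in Arm B only.** With the same true ORR in both arms and independent arms, this is P(1 − P). The rates are those of Section 10.9 and Table 8.

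| True ORR | P (passes gate) | Passes in B only |
|---|---|---|
| 1% (CRC, not of interest) | 0.0956 | 0.0865 |
| 5% (NSCLC, prostate, not of interest) | 0.4013 | 0.2403 |
| 16% (CRC, target) | 0.8251 | 0.1443 |
| 20% (NSCLC, prostate, target) | 0.8926 | 0.0958 |

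**3. At least one of three types open in B only, if the Arm A to Arm B option is always used.**
- Target rates 16/20/20%: 1 − (1 − 0.1443)(1 − 0.0958)² = 0.300.
- Uninteresting rates 1/5/5%: 1 − (1 − 0.0865)(1 − 0.2403)² = 0.473.
- Arm A at the uninteresting rates and Arm B at the target rates: B-only is 0.9044 × 0.8251 = 0.746 for CRC and 0.5987 × 0.8926 = 0.534 for each other type. Then 1 − (1 − 0.746)(1 − 0.534)² = 0.945.

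If the option is never used, the chance that some type is open in just one arm is 1 − Π[1 − 2P(1 − P)]. That is 0.535 at the target rates and 0.777 at the uninteresting rates. A DLT stop of one arm (Section 5.1) is a further route, not counted here.

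**4. Share not randomized.** One type opens in B only with 10 added. Arm A has 30 participants, Arm B has 40, and 10/40 = 25% of Arm B was not randomized.

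**5. Effect on the estimate, with no dose effect.** The documents give no event rates, so these are assumptions.
- Later or selected participants: if the 10 added differ by d points, the shift is d × 10/40. For d = 5, 10 and 20 it is 1.25, 2.5 and 5 points.
- Tumor mix alone: Arm A is 10/10/10 and Arm B 20/10/10. Let the enlarged type have an event rate of 20% to 40% and the other two 10%. At 20% the arms give 13.3% and 15.0%, a difference of +1.7 points. At 40% they give 20% and 25%, a difference of +5.0 points.

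**6. Precision for scale.** The Wald 95% half-width is 1.96 × √[q(1 − q)(1/n₁ + 1/n₂)]. For 30 versus 40 it is 14 points at an assumed q = 10% and 22 points at q = 30%. For 30 versus 30 it is 15 and 23 points.

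**The case against.** - **The rule is discretionary.** Sections 5.1.4 and 10.7 permit expansion or stopping rather than require it, and 5.1.4 lets the sponsor weigh all the data. This stands. The probabilities describe strict use of the response rule and do not forecast conduct.
- **The estimate is descriptive and imprecise.** Section 10.9 rules out formal testing, 10.8 has no multiplicity control, no stopping or expansion rule uses the arm difference, and Section 4 states no between-dose safety objective. A 2.5-point shift is small beside a half-width of 14 to 22 points. This stands and limits the severity. It does not make the estimate a randomized contrast.
- **The sSAP may deal with it.** Sections 10.6 and 10.6.1 defer the comparison between arms to the sSAP, which is not among the documents. But 10.6.2 already fixes the method for the safety difference and says nothing about who enters it.
- **Stronger readings a reader might infer.** One is that sites and patients will know the dose before consent. No section says so, and 10.2 places awareness after enrollment and assignment; advance knowledge is possible, not stated. Another is that the difference uses all treated participants for every endpoint, whereas DLTs have their own evaluable population. A third is that 1:1 also breaks within a type open in both arms (such as 30 versus 10), or that half of Arm B (30/60) is non-randomized with a 5-point shift from a 10-point difference. Those figures require Stage 2 to be filled to 30 per arm. The synopsis and Figure 1 allow that reading, but 5.1 makes 30 an upper limit, 5.1.4 makes 60 per arm a maximum, and 10.9 plans 20 per type per arm.

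**Conclusion.** The point holds as a defect in one stated analysis and an omission in the assignment rule. Under strict use of the response rule, equal response rates, independent arms and the Arm A to Arm B option always used, about 30% (16/20/20%) to 47% (1/5/5%) of such trials would have at least one type open in Arm B only. With the planned 10 added in one such type, a quarter of Arm B would be non-randomized. An assumed 10-point difference in their event rate would then appear as a 2.5-point dose difference; the shift is larger only if the true difference is larger or Stage 2 goes beyond 10 per type.

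The documents do not support reading this as a threat to the trial's decisions. The interim DLT decision uses by-arm counts in the first 10 evaluable participants, and by-arm safety and by-tumor ORR estimates are not contrasts between arms. The change should be made because it is cheap and removes an avoidable confounding from a comparison that the plan says it will report.

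**What to change.** - **Section 10.6.2 and the sSAP arm comparison:** compute the between-dose difference only in participants randomized while both arms were open for their tumor type, stratified by tumor type. Keep the DLT-evaluable restriction for DLTs. Summarize single-arm Stage 2 participants by arm only.
- **Section 7.3, with the synopsis aligned:** state that 1:1 randomization applies to tumor types open in both arms, and that the IRT flags an assignment made while only one arm was open as non-randomized.

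No gate, dose or Stage 2 size has to change, and equal Stage 2 places per arm need not be imposed.

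The cost is some wording, one IRT flag and a somewhat wider interval. In the example above, the Wald half-width goes from 14–22 points (30 versus 40) to 15–23 points (30 versus 30). By-arm summaries lose nothing. If both arms complete Stage 1, at least the 30-versus-30 randomized comparison remains, apart from any participants not evaluable for DLT.
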